4 ANALYSIS SETS

All screened patients will be accounted for in the clinical trial report.

The decisions regarding inclusion/exclusion of patients from the trial analysis sets will be documented in the analysis set definition document before breaking the randomization code.

The following analysis sets are defined in this trial:

4.1 Screened Set

The screened Set will include every patient who has signed informed consent form. The screened Set will be used for summaries of disposition and the associated listing.

4.2 Intention-to-treat Analysis Set

The ITT analysis set will consist of all patients who were randomized to a treatment arm in double-blind treatment period. Analyses based on this population will group patients according to the treatment they were randomized to receive, regardless of actual treatment received.

The efficacy analyses will be primarily based on the ITT analysis set.

4.3 Full Analysis Set

The FAS comprises all patients in the ITT analysis set who were administered at least 1 dose of the IMP. Analyses based on this population will group patients according to the treatment they were randomized to receive, regardless of actual treatment received.

The primary and key secondary efficacy analyses will also be performed based on FAS. If ITT = FAS, the analysis will not be repeated for FAS.

4.4 Per Protocol Analysis Set

The PPS is defined as all patients in the ITT analysis set with no important (major) protocol deviations that would have an impact on the efficacy assessment or any other criterion, as deemed appropriate.

Analyses based on PPS will be of supportive purpose and limited to the primary and key secondary endpoints. Patients will be analyzed according to their actual treatment received.

4.5 Important Protocol Deviations Leading to Exclusion from the Per Protocol Analysis Set

Protocol deviations are defined as any change, divergence, or departure from the trial design or procedures defined in the trial protocol. Important (or major) protocol deviations are protocol deviations that may significantly impact the correctness, accuracy, and/or reliability of the trial data, or that may significantly affect a patient's rights, safety, or well-being.

The criteria to exclude patients from the PPS will be selected based on a blinded review of the data and finalized prior to unblinding of the trial for the primary analysis.

4.5.1 Reporting of Protocol Deviations

All protocol deviations will be periodically reviewed and classified (major or minor) as described in the clinical monitoring plan prior the database lock for the Double-blind Treatment Period. Protocol deviations classified as important (or major) may lead to exclusion from analysis sets, see [Section 4](#).

Major protocol deviations will be summarized by category. All protocol deviations will be listed.

4.6 Pharmacokinetic Analysis Set

The PK analysis set comprises all patients who were administered at least 1 dose of CAM2029 and for whom at least 1 plasma octreotide concentration after the first CAM2029 dose is available.

The PK analysis set will be used for the analyses of PK data.

4.7 Safety Analysis Sets

The SAF comprises all patients who were administered at least one dose of IMP during the double-blind treatment period. Analyses based on this population will group patients according to the actual treatment the patients received.

The safety analyses will be based on the SAF.

5 STATISTICAL ANALYSES

5.1 General Considerations

Three types of data display will be produced for this trial: summary tables, figures, and data listings (also referred to as TFLs), as specified in the sections below.

Unless stated otherwise, data listings will be produced for all recorded data. Additional data listings will be produced for outcome measures that involve extensive procedures to derive the analyzed outcomes. Data listings will simply list the data recorded on the eCRF/vendor data or derived for each patient. Data listings will be ordered by treatment, patient number, and time of assessment if no further preference/hierarchy is specified.

Summary tables will display summary statistics calculated for each of the treatment groups, i.e. CAM2029 Q1W, CAM2029 Q2W, CAM2029, Placebo, and Overall, unless described otherwise in the following sections.

Continuous variables will be summarized with the number of non-missing values, mean, standard deviation, median, minimum, maximum, and quartiles. Categorical variables will be summarized with the number and percentages of patients in each category. Percentages of patients in each of the possible categories will be calculated from the number of patients in the corresponding analysis set, unless stated otherwise in tables, figures, and listings (TFLs). Some continuous variables may also be grouped into categorical levels and evaluated in frequency tables.

Safety parameters will be presented descriptively.

All data processing, summarization and analyses will be performed using SAS Version 9.4 (or later) of the SAS® statistical software package.

Therapeutic interventions with the intention to reduce the liver size included in the estimand definition, will be defined prior to DBL.

5.1.1 Data Sources

Data are recorded on eCRFs. Central laboratory data (including safety, PK, [REDACTED], and immunogenicity), centralized imaging readings, ePRO, eCOA, central ECG, and other imaging data results will be provided via electronic data transfers.

Section 9 of the clinical trial protocol provides additional details regarding data recording and handling.

5.2 Time Points and Visit Windows

5.2.1 Definition of Baseline

Baseline is defined as the last available observed value of the parameter of interest prior to the first administration of IMP during the double-blind treatment period (this includes unscheduled visits). For 12-lead ECG, baseline is defined as the average of the last non-missing triplicate measurements prior to the first administration of IMP. If there are less than 3 measurements, the available measurements will be used.

Change from baseline is calculated as post-baseline value minus the baseline value.

[figure not shown]
Percentage change from baseline is calculated as follows: $(\text{post-baseline result} - \text{baseline result}) / \text{baseline result} * 100$.

5.2.2 Calculation of Trial Day

For any events/assessments on or after the first IMP administration, trial day is calculated as: $\text{event/assessment date} - \text{date of first administration of IMP} + 1$. As such, the first IMP administration date during the treatment period is trial day 1.

For any events/assessments before the first administration date, trial day is calculated as event/assessment date – date of first administration of IMP.

5.2.3 Analysis Visit Window

5.3 Handling of Missing Data

5.3.1 Handling of Missing Efficacy Data

The missing primary and key secondary efficacy data up to Week 53 will be imputed using MI. Imputation will be performed using an FCS regression method.

The procedure for the change from baseline is htTLV is described below.

A regression model will be fitted to the htTLV values at Week 13. The model will include effects of baseline htTLV as a covariate. The estimated parameters and their variances will be used to impute missing htTLV values at Week 13.

Missing htTLV values at Week 25 will be imputed in the same way as Week 13. The model will include effects of baseline htTLV as a covariate together with the htTLV value at Week 13 as a covariate. The estimated parameters and their variances will be used to impute missing values at Week 25.

The procedure will be repeated for missing htTLV values at Week 53 with the modification that htTLV values from the preceding 2 visits will be included as covariates in addition to the baseline htTLV.

Detailed procedures for handling of missing values are included in the sections describing the individual analyses.

5.3.2 Handling of Missing Safety Data

In general, missing clinical laboratory data, vital signs, and ECG data will not be imputed. AE imputations for missing severity or relationship are given in [Section 5.10.1](#). Unknown or partial medication and AE date imputations are given below and to be used only for the assessment of prior / concomitant status for medications and treatment-emergent status for AEs.

5.3.3 Handling of Partial and Missing Dates for Adverse Events, Prior/Concomitant Medication, and IMP Administration

Partial dates may be entered in the eCRF for adverse events and prior and concomitant medications. Dates from these forms will be reported in listings as collected and imputed. Every effort will be made to query missing dates.

AEs that cannot be definitely determined as occurring prior to IMP administration will be counted as TEAEs unless either the partial start date or a partial or complete end date indicates the AE as occurring prior to treatment. Partial dates entered in the AE form will be imputed for the purposes of determining whether the record is a TEAE or not based on the following:

- AE onset dates with missing day and non-missing month will be assumed to occur on the first day of the non-missing month, except for AEs occurring in the month and year of first dosing of IMP, in which case the date will be imputed using the date of first dosing of IMP.
- AE onset dates with missing day and month will be assumed to occur on the first day of the non-missing year (i.e., 01-Jan-YYYY), except for AEs occurring in the year of first

dosing of the IMP, in which case the date will be imputed using the date of the first dosing of IMP.

- Partial or missing AE resolution dates will not be imputed.

Partial dates entered in the Prior and Concomitant Medications form will be imputed for the purposes of determining whether the record is a concomitant or prior medication based on the following:

- Medications that are not ongoing and have a medication stop date with a missing day and non-missing month will be assumed to occur on the last day of the non-missing month.
- Medications that are not ongoing and have a medication stop date with missing day and month will be assumed to occur on the last day of the non-missing year (i.e., 31-Dec-YYYY).
- Partial or missing CM start dates will not be imputed.
- If both start and end/stop dates are missing, then the medication will be classified as concomitant.

If the imputed medication end date is later than the date of last visit, the last visit date will be used as the end date.

5.3.4 Handling of Plasma/Blood Serum Concentrations that are Below the Lower Limit of Quantification

Plasma/blood/serum concentrations that are BLQ will be handled as follows for descriptive statistics:

- Values that are BLQ will be set to the lower limit of quantification for the calculation of summary statistics.

5.4 Treatment Labels

Table 6: Treatment labels for the statistical output

Period	Labels Used in Tables	Order in Table
Double-blind treatment period	CAM2029 Q1W	1
Double-blind treatment period	CAM2029 Q2W	2
Double-blind treatment period	CAM2029	3
Double-blind treatment period	Placebo	4
Double-blind treatment period	Overall	5

5.5 Trial Population

5.5.1 Demographics and Baseline Characteristics

Patient characteristics defined below will be presented in summary tables and data listings for patients in the ITT analysis set. The presentations will be for the following treatment groups:

CAM2029 Q1W, CAM2029 Q2W, CAM2029, Placebo, and Overall. No formal statistical comparisons will be performed.

Demographics:

- Age (years)
- Age group: <65, ≥ 65 years
- Sex
- Childbearing potential (Yes/No. If No, alternatives will be presented))
- Menopausal status
- Race
- Ethnicity

Baseline characteristics:

- Height (cm)
- Weight (kg)
- BMI (kg/m²)
- htTLV (mL/m)
- PLD-S measure score
- eGFR (mL/min/1.73m²)
- Alkaline Phosphatase (IU/L)
- Isolated ADPLD
- PLD associated with ADPKD

5.5.2 Medical History

Medical history will be coded using MedDRA version 25.0 (or a later version, if updated during the trial or in relation to DBL and agreed with the Sponsor). Medical history will be summarized by SOC and PT using frequencies and proportions.

Disease characteristics will also be listed and presented descriptively.

5.6 Patient Disposition

Patient disposition will be summarized as the number and percentage of patients screened, failed screening, randomized, completed the treatment during the double-blind treatment period, discontinued IMP during the double-blind treatment (including reason for IMP discontinuation), continued treatment in the extension period, completed participation in the double-blind treatment period, withdrawal from the trial (including reason for withdrawal), and analysis sets.

The disposition and population inclusion data mentioned above will be listed for all patients. The reasons for being excluded from the analysis sets will also be provided in the listings.

In addition, a separate disposition table summarizing the inclusion/exclusion criteria not met for screen failures will be provided.

5.7 Prior and Concomitant Medications and Non-Pharmacological Procedures

Prior and concomitant medications will be coded using the WHO DD version B3 Global March 2022 (or a later version, if updated during the trial or in relation to DBL and agreed with the Sponsor).

Prior medications are defined as any medications taken and stopped prior to the start of the IMP administration.

Concomitant medications in the treatment period are defined as medications with a start date on or after the first IMP administration or medications with a start date prior to first IMP administration but ongoing or with stop dates on or after first IMP administration.

The following concomitant medication summaries will be produced by WHO-DD ATC classification second level (alphabetically), ATC classification fourth level, and preferred base name with the number and percent of patients by treatment groups and active treatment groups pooled together, presented in double-blind treatment period:

- Concomitant medications ongoing at the first IMP administration or started on or after the first IMP administration
- Concomitant medications with start date after the first IMP administration

The tables will display the number and percentages of patients who reported at least one prior or concomitant medication in each ATC level. Within each ATC level, the tables will display the number and percentages of patients reporting at least one medication as designated by the preferred base name. The outputs will be presented by descending frequency across all patients for a given ATC level and preferred base name. Patients may have more than 1 medication per ATC classification/preferred base name. At each level of summarization, a patient will be counted once if he/she reported one or more medications per ATC classification/preferred base name.

A listing of prior and concomitant medications will also be provided.

Treatments of PLD or its related symptoms, including prophylactic treatments, will be listed and summarized descriptively.

Prior and concomitant non-pharmacological procedures will be coded using MedDRA version 25.0 (or a later version if updated during the trial or in relation to DBL and agreed with the Sponsor), associating LLTs with PTs and SOC by the primary hierarchy.

Prior procedures and concomitant procedures in the treatment period will be defined using similar methods as for prior and concomitant medication above.

Prior and concomitant non-pharmacological procedures will be summarized by SOC, and PT with the number and percent of patients.

A listing of prior and concomitant non-pharmacological procedures will also be provided.

5.8 Extent of Exposure and Treatment Compliance

5.8.1 Extent of Exposure

Exposure to CAM2029 or placebo will be summarized using the following parameters based on the data collected in the EDC system in the double-blind treatment period:

- Treatment duration (in weeks), calculated as the number of weeks the patient received IMP: (date of last dose of IMP within each trial period - date of first dose of IMP + 5 half-lives (i.e., 53 days))/7.
- Total number of injections taken, as documented in the patient diary and the eCRF.

The duration of exposure in weeks will be summarized by treatment arm (including the combined active treatment groups) and overall using descriptive statistics for the safety analysis set. The number and percentage of patients with a cumulative duration of exposure will be presented for the following periods: ≥ 4 weeks, ≥ 8 weeks, ≥ 12 weeks, ≥ 24 weeks, ≥ 36 weeks, and ≥ 52 weeks.

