4.1.2 Double-Blind Treatment Period

Eligible patients will receive their first dose of IMP (CAM2029 or placebo) on Day 1. Patients will be treated with IMP as an SC injection every week for a total of 52 weeks. Patients will be

encouraged to perform self- or partner-administration at home, which is allowed after appropriate training (see [Section 6.2.2](#)).

Following Day 1, there will be at least 6 visits during the 52-week Double-Blind Treatment Period (Weeks 5, 13, 21, 25, 39 and 53) for assessment of efficacy, PK, PD and safety. At Week 2, trial personnel will contact the patients by phone to assess any concomitant medication and AEs. Additional visits may be necessary for training of self- or partner-administration of IMP or for IMP administration by trial personnel if self- or partner-administration is not possible. Where applicable, patients will be offered the possibility to complete trial visits at home. In such cases a nurse will come to the patient's home.

Patients who discontinue IMP treatment during the Double-Blind Treatment Period will continue to be followed in the trial and complete all the assessments up to Week 53 (see [Section 6.10.1](#)). A PK sample and an immunogenicity sample should be collected at least 5 weeks after the last dose of IMP.

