6.10 Discontinuation and Withdrawal Criteria

6.10.1 Discontinuation of Treatment

Patients may voluntarily discontinue from treatment for any reason at any time. If a patient decides to discontinue from treatment, the Investigator must make every effort to determine the primary reason for this decision. The reason for discontinuation should be recorded in the patient's chart and on the appropriate eCRF pages.

Patients who discontinue IMP treatment during the Double-Blind Treatment Period should NOT be considered withdrawn from the trial. Every effort will be made to keep patients who discontinue IMP treatment in the trial. They should return for the assessments indicated in Table 3, up to Week 53. A PK sample and an immunogenicity sample should be collected at least 5 weeks after the last dose of IMP.

If the patients fail to return for these assessments for unknown reasons, every effort (e.g., telephone, email, letter) should be made to contact them. Patients who discontinue IMP treatment during the Extension Period should be asked to complete an End-of-Treatment Visit as soon as possible after the last dose of IMP, and a Safety Follow-Up Visit at least 5 weeks after last dose of IMP.

The Investigator should discontinue a patient's IMP treatment if he/she believes that continuation would be detrimental to the patient's well-being or if the patient experiences an intercurrent illness that compromises the patient's ability to fulfil protocol requirements. The Investigator should contact the Medical Monitor before a patient is discontinued from IMP treatment.

IMP treatment must be discontinued under the following circumstances:

- Development of decreased kidney function as defined by $\text{eGFR} < 25 \text{ mL/min/1.73 m}^2$.
- Pregnancy (see [Section 7.6.1.1](#)).
- Any protocol deviation (including prohibited concomitant therapy, see [Section 6.9.3](#)) that results in a significant risk to the patient's safety or that will interfere with the assessment of the efficacy endpoints of this trial, including significant non-compliance with the trial protocol and procedures.

In addition to the general treatment discontinuation criteria, the toxicity-related criteria listed below will also require IMP treatment discontinuation. The final decision to discontinue IMP treatment is up to the judgment of the Investigator.

Hepatic-related Discontinuation Criteria

- ALT or AST levels $> 8 \times$ upper limit of normal.

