5.8.2 Treatment Compliance

Compliance to CAM2029 or placebo will be summarized using the following parameters based on the data collected in the EDC system in the double-blind treatment period:

- Percent compliance, calculated as:
$$(\text{Total number of injections taken}) / (\text{Total number of planned injections}) \times 100$$

where the total number of planned injections is calculated as the number of weeks that the patient has been treated from Day 1 or the number of weeks from Day 1 to the last completed planned visit, whichever is the last.
- Percent compliance categories, $<80\%$, ≥ 80 and $<120\%$, $\geq 120\%$

The above parameters will be summarized for each treatment group, the combined active treatment groups, and overall (i.e., all treatment groups pooled together). A listing of the exposure and compliance parameters will also be provided. Patient diary data will also be present in listings.

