5.10.1 Adverse Events

AEs will be coded using MedDRA version 25.0 (or higher version if updated during the trial or in relation to DBL and agreed with the Sponsor), associating lowest level terms (LLTs) with PTs and SOC by the primary hierarchy. TEAEs are defined as AEs that started or worsened after the first administration of IMP and to the EOT visit or start of another SRL treatment, whichever comes first. Furthermore, the onset date of an TEAE should be prior to the date of last dose of IMP + 5 half-lives (5x10.6 days).

TEAEs, presented as SOC and PTs, will be further defined:

- Treatment period TEAEs are defined as:
 - For patients enrolled into the extension period: TEAEs that occur or worsen on or after the date of first IMP administration in the treatment period and before the date of the first IMP administration in extension period.
 - For patients early terminated from the IMP in the treatment period: all TEAEs reported are double-blind treatment period TEAEs.

The severity of all AEs will be graded using the latest version of the National Cancer Institute Common Terminology Criteria for Adverse Events (CTCAE). Missing severity will be summarized as a separate category.

IMP-related TEAEs are assessed as “Probably related” and “Possibly related”. If the causal relationship to the IMP is missing, the event will conservatively be assigned as related to IMP.

TEAEs of special interest (TEAESI) will be defined pre-DBL as applicable.

An overall AE summary will be presented using the number and percent of patients, and number of events with the following:

- Any AE
- Any TEAE
- Any IMP-related TEAE, including events assessed as “Probably related” and “Possibly related”, or missing relationship to the IMP on the eCRF
- Any TEAE by CTCAE Grade
- Any IMP-related TEAE of CTCAE Grade ≥ 3
- Any TESAE
- Any IMP-related serious TEAE
- Any TEAEs leading to withdrawal from the trial
- Any TEAE leading to IMP discontinuation, including events with action taken with trial treatment = “Drug withdrawn” on the eCRF and TEAEs leading to withdrawal from the trial

- Any TEAE leading to death, including events with outcome = fatal on the eCRF
- Any TEAESI
- TEAESIs of CTCAE Grade ≥ 3
- Any injection site TEAE
- Any related non-injection site TEAESIs
- Any TEAE related to COVID-19

TEAEs will be summarized by trial period, SOC, and PT, with the number and percentage of patients and the number of events, where applicable.

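### SAP 5.8.1 counts a 53-day washout tail as weeks of receiving IMP, in all arms and past the first extension dose; the SAP 5.8.2 compliance denominator is ambiguous and misleads for patients who stop IMP but stay in follow-up

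*SAP*

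**What the plan says.** SAP 5.8.1 introduces the section with "Exposure to CAM2029 or placebo will be summarized using the following parameters". Treatment duration is "calculated as the number of weeks the patient received IMP", and the formula is "date of last dose of IMP within each trial period - date of first dose of IMP + 5 half-lives (i.e., 53 days))/7". The result is summarized by arm in the safety analysis set and tabulated cumulatively at "≥ 4 weeks, ≥ 8 weeks, ≥ 12 weeks, ≥ 24 weeks, ≥ 36 weeks, and ≥ 52 weeks". The number of injections taken is reported as well.

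The same 53 days appear in SAP 5.10.1, where a treatment-emergent adverse event must start "prior to the date of last dose of IMP + 5 half-lives (5x10.6 days"). That section also ends the double-blind period at the first extension dose for patients who roll over. SAP 5.8.1 has no such cut-off.

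Protocol 4.1.2 has IMP injected "every week for a total of 52 weeks". Under Protocol Table 3 the last double-blind dose is in Week 52, and the first extension dose is at Week 53 (Day 365).

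SAP 5.8.2 defines percent compliance as injections taken over injections planned, "where the total number of planned injections is calculated as the number of weeks that the patient has been treated from Day 1", or as the weeks from Day 1 to the last completed scheduled visit if that is later. Protocol 6.10.1 says of patients who stop IMP in the double-blind period: "They should return for the assessments indicated in Table 3, up to Week 53".

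**The concern.** The label and the formula in SAP 5.8.1 describe different quantities. The label is time on dosing. The formula is time on dosing plus a pharmacokinetic washout, and the washout is added even for patients who received no octreotide. The cumulative table is where a reader looks to see how many patients were treated for a given length of time, and the formula moves patients up its rows without any further injection.

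In SAP 5.8.2, taking the later of two dates means that visits attended off drug add planned injections that were never scheduled to be given. The percentage then reflects whether a patient stayed in follow-up as well as whether doses were missed. The section also does not say whether weeks treated is the tail-inclusive duration of SAP 5.8.1.

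**Working it through.** **Inputs.** Half-life 10.6 days (SAP 5.10.1); tail 53 days and exposure categories (SAP 5.8.1); weekly dosing for 52 weeks (Protocol 4.1.2); last double-blind dose in Week 52 and first extension dose on Day 365 (Protocol Table 3); dosing window ±2 days (Protocol 6.2.1). A dose given on schedule in Week w falls 7(w − 1) days after the first dose.

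**The plan's own figure.** 5 × 10.6 = 53.0 days, so the 53 is not an arithmetic slip.

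**Exposure.** The SAP rule is (7(w − 1) + 53)/7. The comparison column replaces the tail by one 7-day dosing interval.

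| Week of last dose | Days since first dose | SAP 5.8.1 (weeks) | With +7 (weeks) |
|---|---|---|---|
| 1 | 0 | 7.57 | 1 |
| 2 | 7 | 8.57 | 2 |
| 6 | 35 | 12.57 | 6 |
| 18 | 119 | 24.57 | 18 |
| 30 | 203 | 36.57 | 30 |
| 45 | 308 | 51.57 | 45 |
| 46 | 315 | 52.57 | 46 |
| 52 | 357 | 58.57 | 52 |

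Under the SAP rule the 4-, 8-, 12-, 24-, 36- and 52-week rows are first reached with the last dose in Weeks 1, 2, 6, 18, 30 and 46. With +7 they are reached in Weeks 4, 8, 12, 24, 36 and 52. Every duration differs by 53 − 7 = 46 days. The 52-week cut-off stays at Week 46 within the dosing window: Week 45 two days late gives (310 + 53)/7 = 51.86, and Week 46 two days early gives (313 + 53)/7 = 52.29.

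**Overlap with the extension.** A completer's last double-blind dose is on Day 358. The tail ends on Day 358 + 53 = 411, which is 411 − 365 = 46 days after the first extension dose.

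**Effect on the table.** A row count is inflated by patients whose last dose falls between the two cut-offs, for example Weeks 46 to 51 for the 52-week row. With 69/3 = 23 patients per arm, each such patient shifts a row by 1/23 = 4.3 percentage points. The documents do not say how many there will be.

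**Compliance, no dose missed before stopping.**
- Completer attending Week 53, weeks treated without the tail: the denominator is the 52 weeks to that visit, so 52/52 = 100%. This is correct.
- IMP stopped after 12 injections, visits continued to Week 53: weeks treated is at most (77 + 53)/7 = 18.57 even with the tail. The 52 weeks to the visit prevail on either reading, and 12/52 = 23.1%.
- If weeks treated is simply last minus first dose date, a patient dosed at the Week 13 visit and then lost has 13/12 = 108.3%, and a patient with one dose and no later visit has 1/0, which is undefined.

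**The case against.** The best defence is that the tail is deliberate. The product is a depot, Protocol 2.1.2 reports therapeutic levels for about 4 weeks after dosing, the section is titled extent of exposure, and the same five half-lives bound the adverse-event window. A washout-inclusive exposure is a legitimate safety quantity. It stands as something the sponsor may report, but it does not rescue the rule as written. The SAP calls the result weeks of receiving IMP. Placebo has no octreotide to wash out. Arm 2 starts on CAM2029 and alternates weekly (Protocol 6.5.2), so its on-schedule Week 52 injection is placebo and the tail starts from that. For patients who roll over, the adverse-event window closes at the first extension dose while the exposure tail runs on.

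It is also fair to say that the impact is limited. The tail is the same constant in all arms and so creates no between-arm difference in duration. Injection counts, listings and reasons for IMP discontinuation are reported too. SAP 5.10.1 describes counts and percentages of adverse events, with no exposure-adjusted rates. All of this stands.

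A reader might infer more about compliance than the documents support:
- **That the denominator is wrong throughout.** It is right for a completer when the tail is excluded.
- **That a perfect completer scores 52/58.57 = 88.8%, or a patient who leaves after 12 injections 12/18.57 = 64.6%.** Both need the SAP 5.8.1 duration to be carried into SAP 5.8.2, which neither cross-refers to it nor mentions half-lives.
- **That per-protocol membership is affected.** SAP 4.5 leaves the exclusion criteria to a blinded review, and nothing links percent compliance to them.

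Counting injections against the full course could be meant as a persistence measure. The SAP does not say so, and it labels the result compliance.

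**Conclusion.** The exposure point holds. SAP 5.8.1 overstates treatment duration for every patient in every arm, by 46 days relative to a count that gives each weekly injection one week. The 4-week row carries no information, and a patient whose last dose was in Week 46, six weekly injections short of the course, is placed in the full-year row. If every patient completes on schedule, the row counts do not change and only the durations are inflated. The week counts assume on-schedule weekly dosing.

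The compliance point holds in a limited form. The denominator is ambiguous about the tail, and it misleads for patients who stop IMP and remain in follow-up, where 23% can describe someone who missed no scheduled dose before stopping. That result is the same on either reading.

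Both are descriptive outputs. The primary and key secondary analyses do not use them, and the documents show no per-protocol consequence. The change is worth making because it corrects a planned safety table at little cost.

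**What to change.** **SAP 5.8.1.** Define treatment duration in weeks as (last double-blind injection date − first injection date + 7)/7 for all arms. Deleting the tail alone is not enough: an on-schedule completer would have 357/7 = 51.0 weeks, or 358/7 = 51.14 counting both end days, and would miss the 52-week row. Because +7 puts that completer exactly at 52.0, a last dose two days early gives (355 + 7)/7 = 51.7. State whether the top row is assigned by scheduled week or by exact days. Keep the 53 days for the adverse-event window. If washout-inclusive exposure is wanted, report it separately under its own label and cap it at the first extension dose.

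**SAP 5.8.2.** State that weeks treated excludes the tail. Define planned injections as the weekly injections scheduled from Day 1 to the earliest of permanent IMP discontinuation, trial withdrawal, loss to follow-up, or Week 52. State whether doses withheld during protocol-directed interruptions count as planned. Show persistence on IMP separately.

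**Cost.** Two derivation rules in the SAP and their programs, plus a table if persistence or washout-inclusive exposure is added. Reported durations become shorter. SAP section 2 allows modification until database lock and unblinding for the primary analysis.
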